#### Preliminary data

Using data from the Rochester Epidemiology Project, we demonstrated that 30% of AKI Survivors (stage II or III, moderate or severe, respectively) failed to have a serum creatinine assessment and a healthcare visit in the 30-day interval after discharge. These would be considered basic elements of kidney health follow-up. Nephrology visits occurred in less than one-fourth of individuals, even when the time horizon was extended to one year or high-risk patients were considered (i.e., CKD, diabetes) (Manuscript in press at *Am J Nephrol*). Nephrotoxins are also a particular area of concern in AKI survivors, given they are one of few potentially modifiable determinants of long-term complications. We demonstrated that 87% of AKI survivors receive at least one potentially nephrotoxic medication in the 3-years after discharge. Each additional nephrotoxin was associated with a 1.3-fold higher risk of new or progressive CKD within 3-years (Manuscript under review at *Am J Nephrol*).

To address this unmet need for AKI survivor care, we developed the **AKI in Care Transitions (ACT)** intervention with feedback from stakeholders in Nephrology, Pharmacy, Primary Care, Nursing, Informatics, and Administration. The focus is on the delivery of post-AKI care in the patient’s medical home, primary care. This multicomponent strategy includes 1) use of an electronic health record (EHR) indicator to identify high-risk AKI survivors based on biochemical markers (serum creatinine increase, urine output decline), 2) Education about kidney health before discharge by nephrology nurses, 3) kidney function testing in the 7-14-days after discharge, 4) a post-hospital visit by a pharmacist within 7-14-days after discharge, and a 5) post-hospital visit by a primary care provider within 7-14 days after discharge (may be combined with the pharmacist visit). Specialty nephrology follow-up is at the discretion of the inpatient nephrologists or patient’s PCP. The ACT intervention is a transitions of care support strategy where these bundle elements are recommended and made available to the care teams using electronic orders and clinical decision support, but ultimately at the discretion of the treating providers.

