**Patients:** Participants will be recruited from those identified by a developed electronic health record list of patients with AKI. Included individuals that populate the list are those with stage III AKI (severe) during a hospitalization based on serum creatinine rise or urine output decline from Olmsted County. The EHR list which includes these criteria was developed, tested, and refined for accuracy and completeness as part of IRB 20-004204 (see above preliminary data). Screened individuals with dementia, those who are non-English speaking, or expected to dismiss to a skilled nursing facility at discharge will be excluded. Individuals who are expected to need dialysis at discharge or who are discharging on hospice will be excluded. If the patient is actively enrolled in the Primary Care Transitions Program at hospitalization they will be excluded. Recipients of any transplant, including solid organ, hematopoietic stem cell, or CAR-T, within 100-days of enrollment will also be excluded. Individuals may only be enrolled in the trial one time. Trained study team members will approach potential candidates during their hospitalization to obtain written informed consent. Individuals will be provided with information about the research, HIPAA Authorization, and IRB approved consent forms for review. Sufficient time will be allowed for discussion and patient questions. Patients will be informed that declining to participate in the study will not impact the care that they receive. Consent will be obtained in person where possible, but may be obtained via telephone call depending on the safest mode of contact due to

COVID-19. All consenting patients will be included in the clinical trial. No reimbursement or remuneration will be provided for participation.

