"The patient has been enrolled in the ACT (AKI in Care Transitions) trial because they were identified as having biomarker changes consistent with severe AKI (creatinine elevation or oliguria/anuria) and are not expected to leave the hospital on dialysis. They will receive kidney health education from a dedicated team nurse and the ACT team will prepare dismissal orders for a kidney function panel (extended electrolyte panel that includes serum creatinine), a urinalysis with microscopy, a visit with the primary care provider and a visit with an ambulatory care pharmacist for your consideration at dismissal summary signing. Please contact [name] [name] if there are any questions or concerns."

A failsafe EHR clinical decision support tool exists to prompt these dismissal orders for care teams should they be discontinued. Individuals will also be enrolled in a 'care path.' This tool operates based on embedded rules in the EHR to deliver context appropriate prompts and resources for providers. The benefits of a 'care path' is that it is not affiliated with a specific encounter. It remains active for the patient regardless of setting (inpatient or outpatient) until the rule-based criteria are fulfilled (i.e., education delivered, visits ordered and scheduled, visits and tests completed). In the post-hospital primary care provider and pharmacist visits, a passive Epic 'best practice advisory' has been created to encourage care providers to address kidney function, education, medication management, blood pressure assessment and sick day counseling. Institutional provider or patient resources on AKI survivor care are available for use in these visits (<http://intranet.mayo.edu/charlie/nephrology-hypertension-rst/education/patient/> , <https://askmayoexpert.mayoclinic.org/topic/clinical-answers/cnt-20114555/sec-20114604> ). A structured documentation template for visits has been developed. If deemed appropriate, nephrology referral will be coordinated by the PCP.

Control. Participants in the control group will receive no specific study-related intervention. AKI identification, patient education, and follow-up care will be at the discretion of the primary treating team. It is customary for these patients to receive some degree of laboratory monitoring and clinical follow-up in the post-

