### Data collection

Individuals that consent to participate will be captured in the REDCap system. Those found to be ineligible or eligible but decline participation will be captured in a recruitment tracking log. Data sources for the study include medical record review, interviews, and direct observations or video/audio recordings of the clinical encounters. An overview of the data collection plan is outlined in **Table 1**.

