Data will be abstracted from the EHR on patient demographics, comorbidities, attributes of the hospitalization, details about the episode of AKI and the degree of recovery by discharge, follow-up processes of care (laboratory assessments, visits), and clinical outcomes. Core data to be collected will include age, sex, height, weight, race/ethnicity, socioeconomic status, health literacy (using the Brief Health Literacy Screen), history of hypertension, diabetes, cardiovascular disease, chronic kidney disease, or other vascular diseases, hospital and intensive care unit length of stay, reason for admission (non-operative, operative), discharge disposition, whether nephrology was involved with the patient's care during the hospitalization, the severity of AKI, need for dialysis, and discharge kidney function. Select medication data will be collected at baseline (preadmission based on the documented medication list in the EHR), discharge, and 30-day follow-up. This will include the use of angiotensin converting enzyme inhibitors/angiotensin receptor blockers (ACEi/ARBs), sodium glucose co-transporter 2 inhibitors (SGLT2i), metformin, GLP-1 receptor antagonists, sulfonylureas, insulin, loop diuretics, thiazide diuretics, statins, aspirin, non-steroidal antiinflammatory drugs (NSAIDs). The total number of medications at discharge will be evaluated. Using previously described methods, EHR documentation for patients who complete a follow-up encounter with a health care provider (provider, pharmacist, or other), will be reviewed to identify medication discrepancies and drug therapy problems. These will be catalogued for all medications and specifically nephrotoxic or renoprotective medications. Drug therapy problems will be categorized as pertaining to effectiveness, indication, safety, or adherence. Additional data elements may be abstracted from the electronic health record to support the study aims. Data will be collected in a secure REDCap database designed expressly for this study. REDCap (<https://redcap.mayo.edu/redcap/index.php>) is a secure, web-based application that is HIPA compliant and available 24 hours per day. Data will be managed by the trial statistician and the principal investigator.

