**Clinical and process outcomes:** Participants will be followed for 1 year post-discharge or until death or loss of follow-up within that timeframe. At 90-days, clinical outcomes to be assessed include Major Acute Kidney Event (MAKE) at 90-days, unplanned emergency department visit or rehospitalization. Incidence of de novo or progressive chronic kidney disease or death up to 12-months after discharge will be documented. Number of nephrotoxic medications, medication discrepancies, and drug therapy problems will be described. Process outcomes will include kidney laboratory assessments and their timing, clinician visits (e.g. with primary care provider, pharmacist, nephrologist), visit type (in-person vs telemedicine/virtual), and timing.

**Table 1.** Summary of study measures

Element	Source	Admission	Randomization	Discharge	Study follow-up visit (intervention patients only)	30-days	90-days	1-year
Sociodemographic factors, comorbidities	EHR	X						
Attributes of hospitalization and AKI episode	EHR			X				
Medication utilization	EHR	X		X		X		
Brief Health Literacy screen	Patient self-report		X					
mKiKS	Patient self-report		X			X		

PROMIS 10	Patient self-report		X			X		
Was it worth it?	Patient self-report					X a		
Encounter observation +/- video/audio recording	Direct observation					X a		
Qualitative interviews	Patient or clinician self report					X a		
MAKE, unplanned ED visit, rehospitalization	EHR						X	
CKD or death	EHR							X
Kidney laboratory assessments, outpatient clinician visits	EHR						X	

a: Intervention patients only

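### Labs, visits and events come from the EHR alone, and ACT follow-up is tracked more closely than control follow-up, so unequal capture of outside care could favour ACT on process outcomes

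*Combined protocol and SAP*

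**What the plan says.** **Source of outcomes.** The Outcomes section says "Process outcomes will include kidney laboratory assessments and their timing, clinician visits". Table 1 lists the EHR as the sole source for these at 90 days, for the row "MAKE, unplanned ED visit, rehospitalization" at 90 days, and for CKD or death at one year. The Data collection section agrees: what is abstracted from the EHR includes "follow-up processes of care (laboratory assessments, visits), and clinical outcomes". The same section gives the full list of sources: "Data sources for the study include medical record review, interviews, and direct observations or video/audio recordings of the clinical encounters". No section mentions records from other institutions, a linked regional source, a death index, or asking patients about care elsewhere.

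**Who is enrolled.** Under Sample, recruitment, "Included individuals that populate the list are those with stage III AKI (severe) during a hospitalization", with the further condition "from Olmsted County". Having a primary care provider inside the institution is not a stated criterion.

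**How follow-up arises in each arm.** For ACT patients, the Intervention paragraphs describe coordinated appointments for laboratory tests, a primary care visit and a pharmacist visit. An EHR care path stays open until these are completed. The Outcomes section adds that reasons for not completing the bundle will be characterized. For controls, "AKI identification, patient education, and follow-up care will be at the discretion of the primary treating team", and neither the timing nor the content of follow-up is fixed.

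**Background rate.** The Preliminary data section reports "Using data from the Rochester Epidemiology Project, we demonstrated that 30% of AKI Survivors" (stage II or III) lacked a creatinine measurement and a healthcare visit within 30 days of discharge. The trial does not name that data source for its own outcomes.

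**The concern.** Random assignment determines both the care a patient is offered and how closely the completion of that care is watched. If an ACT patient's visit is not seen in the EHR, the care path stays open and the study team looks for the reason. No equivalent process is described for a control patient whose visit is not seen. Randomization balances where patients usually get care; it does not balance a difference in tracking that begins after assignment.

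Processes of care are named in the Aim 2 hypothesis, and the Sample Size section says the results will inform later studies. If control follow-up is under-recorded more than ACT follow-up, the pilot would overstate the gain in follow-up and pass that figure to the next design. For clinical events, the same inequality would make controls appear to have fewer events.

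**Working it through.** **The plan's own figure.** The only design calculation concerns the knowledge score: a 12.5% difference, SD 15%, two-sided alpha 0.05, 80% power. The normal approximation gives n = 2 × (1.96 + 0.842)² × (15/12.5)² = 22.6, so 23 per group. The noncentral t gives 24, and 25 per group has 82.3% power. The stated 25 is reproduced. That score is collected directly from patients in both arms, so it does not depend on EHR capture. The plan gives no figure for capture.

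**Inputs for the process outcomes.**
- True share with creatinine and a visit: p = 0.70 in both arms. This is the complement of the 30% in Preliminary data, and is an assumption. That figure covers stage II–III AKI at 30 days, whereas the trial enrols stage III and Table 1 assesses labs and visits at 90 days.
- Capture share by arm, c_A (ACT) and c_C (control): not given in the documents, so a range is assumed.

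**Formula.** Observed rate = p × c. With no true effect, spurious difference = p × (c_A − c_C).

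| ACT capture | Control capture | Observed ACT | Observed control | Spurious difference |
|---|---|---|---|---|
| 100% | 95% | 70.0% | 66.5% | 3.5 points |
| 100% | 90% | 70.0% | 63.0% | 7 points |
| 100% | 80% | 70.0% | 56.0% | 14 points |
| 90% | 80% | 63.0% | 56.0% | 7 points |
| 90% | 90% | 63.0% | 63.0% | 0 |
| 90% | 100% | 63.0% | 70.0% | −7 points |

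Only the gap in capture matters: each 10 points of gap moves the comparison by 0.70 × 10 = 7 points. Full ACT capture is not needed for a bias, and equal loss in both arms produces none.

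**Against the precision of the pilot.** At 25 per arm, 14 points is 17.5 against 14.0 patients. The standard error of that difference is √(0.70 × 0.30/25 + 0.56 × 0.44/25) = √0.018256 = 0.135, so the artefact is about one standard error. It would reach p < 0.05 about 17% of the time. The harm is to the estimate more than to the test.

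**Clinical events.** Take the 49% one-year rehospitalization quoted in Background and Significance as true in both arms (an assumption). The apparent hazard ratio is approximately ln(1 − p·c_A)/ln(1 − p·c_C).
- 100% against 80% capture: ln(0.510)/ln(0.608) = 1.35, against ACT.
- 95% against 85%: ln(0.5345)/ln(0.5835) = 1.16, against ACT.
- Equal capture: 1.0.

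These show what unequal capture would do. They do not show that it occurs: the study schedules emergency visits and admissions in neither arm. For CKD and the kidney-function part of MAKE, more testing in ACT could also detect more cases.

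**The case against.** The strongest reply is that no asymmetry has been shown. Assignment is 1:1 by patient, so patients with an outside primary care provider should be equally common in both arms. ACT is delivered through the patient's own primary care, so an ACT patient with an outside provider may also have a visit the EHR does not show. If providers are in-house, control visits are visible too, and the documents lean that way: the control paragraph says providers can use materials on the institution's intranet, and buy-in was obtained from the institution's own primary care groups.

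A reader might infer that ACT care is always seen, that outside care of controls leaves no trace, and that the comparison is therefore biased. The documents do not support this. ACT elements remain discretionary, and only 6 of 8 pilot patients (75%) completed a pharmacist encounter. The text says EHR without saying whether outside records can be viewed in it. The 3.5 to 14 points restate an assumed loss confined to controls. The plan also schedules no comparison with the 30% background figure, so a mismatch of data sources harms no stated analysis.

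All of this stands and limits the claim to a risk. It does not remove the difference in tracking, which begins after randomization. Nor does the plan measure capture, so the reassuring reading cannot be verified from the data to be collected.

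**Conclusion.** The point holds as a conditional one. With the EHR as sole source, no in-house care requirement, and follow-up actively tracked in one arm only, unequal capture is a structural risk to the process comparison. If controls are captured less completely, process outcomes favour ACT by 7 points per 10-point gap in capture, assuming a true 70% in both arms. With equal capture the bias is zero. For clinical events the direction is uncertain. The knowledge score is unaffected, and the feasibility proportion is measured in ACT patients only, so it involves no contrast between arms. These are preliminary estimates from a 50-patient pilot. The point is therefore a worthwhile, inexpensive improvement and does not undermine the trial.

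**What to change.** 1. At the 30 ± 7 day contact already planned for every patient, ask both arms the same scripted question: any laboratory tests, clinician visits, emergency visits, admissions or dialysis elsewhere since discharge. Record the answers in REDCap and add the item to Table 1.
2. State in Data collection whether the EHR shows records from other institutions. If it does, search them by one written procedure in both arms, through 90 days and one year.
3. Add the Rochester Epidemiology Project as an outcome source if the sponsor confirms that it covers care outside the institution; the documents do not say.
4. Report process outcomes by arm, with and without the added sources, so that the effect of capture is visible.

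Cost: a few extra minutes on a contact estimated at 15 minutes, in 50 patients, plus one search procedure. The cost of item 3 cannot be judged from the documents. Self-report is imperfect, though it is asked alike in both arms. The 30-day question does not cover later events, which rest on items 2 and 3. It has to be in place before the contacts occur, since the 30-day answers cannot be recovered afterwards.

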### Statistical analysis

**Analysis plan:** To describe the feasibility of ACT and generate preliminary estimates of the effect on patient reported and clinical outcomes, descriptive analyses will be conducted in three groups 1) the intention to treat population (anyone randomized), 2) the per protocol population (randomized patients who receive the assigned study intervention; in the case of ACT patients this would include completion of nurse education, laboratory testing, pharmacist visit, and primary care provider visit), and 3) the complete follow-up population (the per protocol population with follow-up patient reported outcomes at 30 +/- 7 days). Baseline characteristics will be described with means and standard deviations and counts and percentages and compared using t-tests and chi-squared tests, respectively. Any baseline imbalances ( $p < 0.05$ ) will be explored as a possible factor to adjust for when the outcome measures are analyzed. The CONSORT guidelines will be followed to transparently report study results.

AKI knowledge will be described between groups with the mean mKiKS score. In patients with incomplete follow-up, model imputation will be used to impute follow-up scores. Mean between-group differences in the total baseline and follow-up scores will be compared using the t-test or non-parametric Mann Whitney U test. An exploratory multivariable linear regression model will be fit with group assignment as the independent predictor of interest, mean follow-up knowledge scores as the dependent variable, and baseline scores as a covariate. Other variables to be considered will include age, sex, baseline health literacy, socioeconomic status, and baseline comorbidities, specifically CKD. Clinical outcomes up to 12-months will be compared with Cox proportional hazards models.

**Sample Size:** As a pilot clinical trial, we will include all eligible candidates during the enrollment period. Based on preliminary feasibility data, we estimate approximately 1-2 patients per week will be identified with the EHR trigger, of which 70% will be eligible, agree to participate in the trial, and have evaluable outcomes data. We, therefore, estimate enrollment of approximately 25 patients per group (50 total) during the 18-month study timeframe. A sample size of 25 participants per group would be sufficient to detect a mean difference of 2 points on the mKiKS score (12.5%), using a two-tailed alpha of 0.05 and 80% power, assuming a standard deviation of 15%. Results from this study will provide the necessary pilot data to inform future investigations.

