## Research Question and Aims

**Aim 1: Evaluate the feasibility and acceptability of the AKI in Care Transitions pilot and iteratively refine the intervention.** Feasibility of the pilot will be quantified by the percentage of randomized AKI survivors who receive the full ACT intervention (nurse education visit, laboratory testing, pharmacist visit, primary care provider visit). Using encounter video recordings, and qualitative interviews with patients and clinicians, we will assess user interactions with the pilot intervention, tool fidelity, and acceptability of the intervention for patients and clinicians. Based on identified barriers and facilitators, the intervention will be iteratively refined for scaling and testing in a larger prospective clinical trial.

**Aim 2: Generate preliminary estimates of the ACT intervention on clinical and patient-reported outcomes.** We will conduct a pilot clinical trial in 50 patients over 18-months. Patients with severe AKI will be randomized 1:1 (25 per group) to either the control group (usual care) or the intervention group (ACT). In the intention-to-treat population, we will assess change in AKI knowledge from baseline to 30-days using a validated scale. Differences in other patient-reported and clinical outcomes will be characterized. The use of nephrotoxins will be quantified from reconciled medication lists. We *hypothesize* that the intervention group will experience improved AKI-related knowledge, processes of care, and outcomes compared to control patients.

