Randomization: Should the patient consent to participate, the individual will randomly be assigned 1:1 to one of two groups, the ACT group (intervention) or usual care (control). Randomization will occur via sealed envelopes which will contain the randomization information. Based on our preliminary data, randomization will be stratified according to hospital service/source: hospital medicine/family medicine or other services. Individuals will be randomly allocated equally to the intervention or control groups within each stratum using a permuted block design with varying block sizes of between 2 and 4. The target sample size is 50 (25 per group). The study coordinator will disclose the group allocation to patients after completing standard informed consent for participation in clinical research including permission to use protected health information.

Intervention: The ACT intervention was approved by the Mayo Midwest Clinical Practice Committee and local discipline specific subcommittees (nephrology, primary care, pharmacy). The intervention workflow was developed and pilot tested as part of IRB 20-004204. A description of the intervention is undergoing peer-review for publication ([name], et al.). As outlined in the preliminary data, patients randomized to the ACT intervention receive a multicomponent transitional support bundle including 1) a consultation from nurse educators before discharge to deliver kidney health education using approved materials available for use by any Mayo Clinic provider or patient (<http://intranet.mayo.edu/charlie/nephrology-hypertension-rst/education/patient/> , <https://askmayoexpert.mayoclinic.org/topic/clinical-answers/cnt-20114555/sec-20114604> ), 2) coordinated appointments for post-discharge laboratory testing (serum creatinine and urinalysis with microscopy), a primary care provider visit, and a pharmacist visit within approximately two weeks of discharge. Each of these elements would be considered standard for an AKI survivor, but the ACT intervention aims to operationalize them more cohesively and consistently to facilitate the care transition. A note will be entered into the patient's EHR to communicate enrollment to the healthcare providers. As an example, a note that may be entered for an intervention patient could be as follows:

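### A p<0.05 baseline screen nominates adjustment factors, while the exploratory mKiKS regression leaves five factors optional and does not name the randomisation stratum (minor)

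*Combined protocol and SAP*

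**What the plan says.** The Analysis plan paragraph under Statistical analysis says that baseline characteristics will be "compared using t-tests and chi-squared tests, respectively". It then says that any imbalance at p<0.05 "will be explored as a possible factor to adjust for when the outcome measures are analyzed". It does not say what exploring involves, what would let a flagged variable into a model, or how many characteristics are tested. The sentence is not limited to one outcome, so it also reaches the Cox models for clinical outcomes, for which no covariates are named.

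For AKI knowledge the plan has an unadjusted t-test or Mann-Whitney comparison, and then a regression: "An exploratory multivariable linear regression model will be fit with group assignment as the independent predictor of interest". Baseline mKiKS is a fixed covariate. Beyond that, "Other variables to be considered will include age, sex, baseline health literacy, socioeconomic status, and baseline comorbidities, specifically CKD". No entry rule follows.

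The Randomization paragraph, under Sample, recruitment, says that "randomization will be stratified according to hospital service/source: hospital medicine/family medicine or other services", with allocation "within each stratum using a permuted block design with varying block sizes of between 2 and 4". Hospital service is not named as a term in any analysis.

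Aim 2 is to "Generate preliminary estimates of the ACT intervention on clinical and patient-reported outcomes".

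**The concern.** A significance test between randomised arms asks whether chance produced the difference, and under correct randomisation the answer is already known. What matters for adjustment is whether a variable predicts the outcome, and the test does not address that. A screen at p<0.05 can therefore nominate irrelevant variables and pass over a prognostic variable with a moderate imbalance. In the per-protocol and complete-follow-up sets, differences can also come from selection after randomisation, but a p-value threshold does not repair that either.

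The mKiKS regression has a related gap. Five factors may or may not enter, and the one factor the design itself uses, hospital service, is not named. Blocking within service makes it unlikely that the screen would bring it in. At stake is the adjusted effect estimate that Aim 2 is meant to supply: it depends on choices left until the data are seen, and its standard error is overstated if service is prognostic and omitted.

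**Working it through.** **1. The plan's own figure.** The Sample Size paragraph gives a 2-point difference (12.5%), SD 15%, two-sided alpha 0.05, 80% power and 25 per group. Normal approximation: n = 2 × (1.960 + 0.842)² × (15/12.5)² = 2 × 7.85 × 1.44 = 22.6, so 23 per group. The t-test needs 24, and 25 per group gives 82.3% power. The figure reproduces on an unadjusted comparison, so this point does not touch it. The implied scale is 2/0.125 = 16 points, so the SD is 0.15 × 16 = 2.4 points.

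**2. What the screen can see.** With 25 per arm, the smallest continuous difference that reaches p<0.05 is 2.011 × √(2/25) = 0.57 SD. The number of tests is not stated. For an assumed 12 to 29 tests, the expected number of chance flags is 12 × 0.05 = 0.60 to 29 × 0.05 = 1.45. If the tests were independent, the chance of at least one flag would be 1 − 0.95¹² = 46% to 1 − 0.95²⁹ = 77%. Several listed characteristics overlap (diabetes and metformin, for example), which would lower these last two figures.

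**3. Whether the screen would pick up the stratum.** With blocks of 2 and 4, the arms differ by at most 2 patients within a stratum. Take strata of 26 (14 against 12) and 24 (11 against 13): chi-squared = 50 × (14×13 − 11×12)² / (25 × 25 × 26 × 24) = 0.32, p = 0.57. That is far from a flag.

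**4. Cost of the screen.** The documents give no correlations. The simulation assumes n=50, two strata, blocks of 2 and 4, correlation 0.5 between baseline and follow-up mKiKS, one other factor with partial correlation 0.3, and a true difference of 2 points (12,000 runs). Baseline mKiKS is in every model. Each cell is the empirical SE in points, then power.

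| Rule for flagged variables | 12 tests | 29 tests |
|---|---|---|
| None entered | 0.591, 91.2% | 0.599, 90.2% |
| Kept if associated with outcome, p<0.05 | 0.591, 91.2% | 0.609, 90.0% |
| Kept if associated with outcome, p<0.10 | 0.593, 91.1% | 0.616, 89.6% |
| All entered | 0.607, 89.0% | 0.644, 85.3% |

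Compare within columns only; the two top-row values differ by simulation noise. If flagged variables are kept only when associated with outcome, the SE rises by 0% (0.591/0.591) to 3% (0.616/0.599), and power changes by less than 1 point. Entering every flag costs 3% with 12 tests and about 7.5% with 29 (0.644/0.599).

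Type I error with 29 tests (8,000 runs, Monte Carlo SE 0.25 points) was 5.6% with none entered, 5.2% with all entered, and 5.7% and 5.9% under the two keep rules. The first should be 5%, so its excess is noise. Relative to it the rules move the rate by −0.4 to +0.3 points.

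**5. Stratum left out.** The variance left after baseline mKiKS is 2.4² × (1 − 0.5²) = 4.32. With equal strata, a share s of it corresponds to a difference between services of 2 × √(4.32 s). From 15,000 null runs:

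| Share s | Difference between services | Type I error without stratum | With stratum |
|---|---|---|---|
| 0% | 0 | 4.95% | 4.95% |
| 10% | 1.3 points | 4.05% | 4.99% |
| 20% | 1.9 points | 2.95% | 4.99% |
| 30% | 2.3 points | 2.14% | 5.11% |

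At 10% the model SE is 0.591 against an empirical 0.565, an overstatement of 5%. This agrees with the approximation 1/√(1 − 0.10) = 1.05. A 30:70 split of strata gives nearly the same rates (5.01, 3.97, 2.82 and 2.19%). A separate simulation with a 0.5 SD stratum effect (0.5 × 2.4 = 1.2 points) put the power loss at about 1 point (92.1% against 93.3%).

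**6. The optional factors.** Five in-or-out choices give 2⁵ = 32 models. In 4,000 null runs with none, one or two factors prognostic (partial correlation 0.3), the median spread of the estimate across the 32 models was 0.26, 0.34 or 0.42 points. Always reporting the smallest p-value would give type I error of 7.9, 9.9 or 11.2%.

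**The case against.** The plan calls its analyses descriptive and this regression exploratory, in a pilot. The strongest likely predictor, baseline mKiKS, is already fixed, and the unadjusted comparison stands whatever the screen shows. All of this holds and limits the point to minor.

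Four stronger readings are tempting, and the documents do not support them.

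- A reader might infer that every flagged variable enters the model. The text says only that it is explored as a possible factor, so the 7.5% SE loss needs both 29 tests and a rule the plan does not state.
- A reader might infer that the screen biases the estimate or inflates type I error. It does neither to any material degree.
- A reader might infer that the analysts will search the 32 models for the best result. Nothing proposes this, and the plan commits to transparent CONSORT reporting. The error rates of 8-11% are a hypothetical worst case. The five factors can even be read as the intended covariate list.
- A reader might infer that the stratum is excluded. The list is open, so it is unnamed, not ruled out. The 20% and 30% shares are stress cases, since they need services to differ by about as much as the 2-point target.

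What stands is that the entry of covariates is undecided, that the stated criterion for nominating them is uninformative, and that the design's own stratification factor has no stated place in the analysis.

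**Conclusion.** The point holds as a minor one. The wording is clear, so confidence in the textual finding is high; the size rests on assumed correlations and an assumed number of tests. On those assumptions the screen's likely cost is an SE 0-3% larger. Omitting the stratum costs nothing if it is not prognostic. If it explains 10% of residual variance, the test becomes conservative, at about 4% in place of 5%. Neither effect biases the estimate on average, and the sample size is unaffected. The practical gain from a change is that the adjusted estimate no longer depends on choices made after the data are seen. Nothing was quantified for the Cox models.

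**What to change.** - Delete the baseline significance tests and the p<0.05 rule for all outcome measures, and present baseline data descriptively.
- Fit the mKiKS regression with group, baseline mKiKS and hospital-service stratum, plus a set of the already named pre-randomisation factors chosen in advance and entered whatever their observed balance. A subset or the full list would do, since either removes the discretion.
- Stratify the Cox models by hospital service, with no covariates selected by the screen.
- Label any other adjustment as a sensitivity analysis.

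The change is to wording only and needs no patients or data. In the 12-test setting above, the stratum term takes one degree of freedom and costs no measurable precision when it is not prognostic (SE 0.591 with and without). One added non-prognostic factor raises the SE to 0.597 (1%) and two to 0.604 (2%); one with partial correlation 0.3 lowers it to 0.569 (4%). Entering all five named factors raised the SE by about 5% when none was prognostic, with type I error of 4.8-5.4% (3,000 runs).
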